#### *Sample Collection*

For microRNA analysis, peripheral blood will be collected in two 10-ml EDTA lavender top tubes and one 2.5-ml PAXgene tube at baseline and post-treatment, if feasible. Blood samples will be held at room temperature and picked up by [name] lab. Contact study team for PAXgene tube.

### **1.17.7 Tumor Gene Expression**

In addition to acquiring resistance through enrichment or acquisition of genomic alterations, resistance may also arise through adaptive cellular responses in the absence of identifiable genomic alterations. This can best be evaluated through evaluation of tumor gene expression. Total RNA will be isolated from matched tumor tissue both before and after therapy, reverse transcribed, and used for transcriptome analysis. RNA will be isolated from matched FFPE cores (MR 1.1a and MR 2.1a). Additionally, RNA may be isolated from involved tissue in the prostatectomy specimen after completion of clinical diagnostic evaluation by the Laboratory of Pathology, as described above. Transcriptome sequencing and analysis will be done using approved protocols under the auspices of [name] in the Laboratory for Genitourinary Cancer Pathogenesis, CCR.

#### *Sample Collection*

Pretreatment screening biopsy samples will be received by Laboratory of Pathology and processed in standard fashion using formalin fixation and paraffin embedding. Post-treatment biopsy samples will be obtained by Laboratory of Pathology and processed in standard fashion using formalin fixation and paraffin embedding, as described above. Biopsy samples and, if appropriate, adjacent areas of the prostatectomy specimen, will be used for molecular studies after completion of clinical diagnostic evaluation. To enrich for tumor cell purity, it is expected tumor specimens will undergo microdissection prior to isolation of RNA and preparation of sequencing libraries.

### **1.17.8 Management of Results**

The results of molecular studies conducted using specimens collected on this protocol are for research purposes only and will not be disclosed to individual subjects. The exception to this is potential incidental findings that are deemed medically significant and actionable. The policy for this disclosure is outlined below and in the consent form for this study.

Subjects will be contacted if a clinically actionable gene variant is discovered. Clinically actionable findings for the purpose of this study are defined as disorders appearing in the American College of Medical Genetics and Genomics recommendations for the return of incidental findings that is current at the time of primary analysis. (A list of current guidelines is maintained on the CCR intranet:

<https://ccrod.cancer.gov/confluence/display/CCRCRO/Incidental+Findings+Lists>). Inherited alterations that may contribute to disease susceptibility in addition to prostate cancer may also be uncovered. Subjects will be contacted at this time with a request to provide a blood sample to be sent to a CLIA certified laboratory. If the research findings are verified in the CLIA certified lab, the subject will be offered the opportunity to come to NIH (at our expense) to have genetic education and counseling to explain this result. If the subject does not want to come to NIH, a referral to a local genetic healthcare provider will be provided (at their expense).

This is the only time during the course of the study that incidental findings will be returned. No interrogations regarding clinically actionable findings will be made after the primary analysis.

Subject's genetic data may be deposited in a database such as dbGaP. Although there is controlled access to such a database, such a submission carries theoretical risks of revealing the identity of the subject. This is discussed in the consent.

### **1.17.9 Comparison of pathology to imaging**

The use of a patient-specific mold (as described in Section 1.2.6.) allows the radical prostatectomy specimen will be sectioned in the same plane as the MRI scans (see Section 3.4.1 and 3.4.2), and thus any immunohistochemistry (IHC) performed (see Sections 5.1.1 and 5.1.2) may help to inform analysis or interpretation of MRI in the post-treatment setting. There are no commercial software packages that specifically address the issue of automated quantification of post-treatment IHC and alignment with MRI. Drs. [name], [name], and [name] in the Molecular Imaging Program will collaborate with Drs. [name] in the Laboratory of Genitourinary Cancer Pathogenesis to identify appropriate programs and tools for assessing correlation. As necessary, collaborations with third parties (including academic centers and commercial manufacturers of quantitative software) may be sought for finding the optimal solution. If a collaboration with an external party is to be sought, a personnel change amendment to this protocol will be made. All data shared with third parties will be coded, linked and covered under a human-materials MTA written specifically for each collaboration (see Section 9.1).

## **1.18 SAMPLE STORAGE, TRACKING AND DISPOSITION**

Samples will be ordered in CRIS and tracked through a Clinical Trial Data Management system. Should a CRIS screen not be available, the CRIS downtime procedures will be followed. Samples will not be sent outside NIH appropriate approvals and/or agreements, if required.

All specimens obtained in the protocol are used as defined in the protocol. Any specimens that are remaining at the completion of the protocol will be stored in the conditions described below. The study will remain open so long as sample or data analysis continues. Samples from consenting subjects will be stored until they are no longer of scientific value or if a subject withdraws consent for their continued use, at which time they will be destroyed. The PI will record any loss or unanticipated destruction of samples as a deviation. Reporting will be per the requirements of Section 7.2.

### **1.18.1 Sample Data Collection - Blood Processing Core (BPC)**

Please e-mail [[contact]](mailto:[contact]) at least 24 hours before transporting samples (the Friday before is preferred).

For sample pickup, page [name].

For immediate help, call [contact] (main blood processing core number) or, if no answer, [contact] (main clinical pharmacology lab number).

For questions regarding sample processing, contact [[contact]](mailto:[contact]).

All samples sent to the Blood Processing Core (BPC) will be barcoded, with data entered and stored in the Labmatrix utilized by the BPC. This is a secure program, with access to Labmatrix limited to defined [name] lab personnel, who are issued individual user accounts. Installation of Labmatrix is limited to computers specified by [name]. These computers all have a password restricted login screen.

Labmatrix creates a unique barcode ID for every sample and sample box, which cannot be traced back to patients without Labmatrix access. The data recorded for each sample includes the patient ID, name, trial name/protocol number, time drawn, cycle time point, dose, material type, as well as box and freezer location. Patient demographics associated with the clinical center

**Abbreviated Title:** Neoadjuvant ADT & Enzalutamide

**Version Date:** 01/25/2024

patient number are provided in the system. For each sample, there are notes associated with the processing method (delay in sample processing, storage conditions on the ward, etc.).

### **1.18.2 Sample Storage and Destruction**

Barcoded samples are stored in barcoded boxes in a locked freezer at either -20 or -80°C according to stability requirements. These freezers are located onsite in the BPC and offsite at NCI Frederick Central Repository Services in Frederick, MD. Visitors to the laboratory are required to be accompanied by laboratory staff at all times.

Access to stored clinical samples is restricted. Samples will be stored until requested by a researcher named on the protocol. All requests are monitored and tracked in Labmatrix. All researchers are required to sign a form stating that the samples are only to be used for research purposes associated with this trial (as per the IRB approved protocol) and that any unused samples must be returned to the BPC. It is the responsibility of the NCI Principal Investigator to ensure that the samples requested are being used in a manner consistent with IRB approval.

Following completion of this study, samples will remain in storage as detailed above. Access to these samples will only be granted following IRB approval of an additional protocol, granting the rights to use the material.

If, at any time, a patient withdraws from the study and does not wish for their existing samples to be utilized, the individual must provide a written request. Following receipt of this request, the samples will be destroyed. The PI will record any loss or unanticipated destruction of samples as a deviation. Reporting will be per requirements of Section **7.2.1**.

Sample barcodes are linked to patient demographics and limited clinical information. This information will only be provided to investigators listed on this protocol, via registered use of the Labmatrix. It is critical that the sample remains linked to patient information such as race, age, dates of diagnosis and death, and histological information about the tumor, in order to correlate genotype with these variables.

## **DATA COLLECTION AND EVALUATION**

### **1.19 DATA COLLECTION**

The PI will be responsible for overseeing entry of data into a 21 CFR Part 11-compliant data capture system provided by the NCI CCR and ensuring data accuracy, consistency and timeliness. The principal investigator, associate investigators/research nurses and/or a contracted data manager will assist with the data management efforts. Primary and final analyzed data will have identifiers so that research data can be attributed to an individual human subject participant.

All adverse events, including clinically significant abnormal findings on laboratory evaluations, regardless of severity, will be followed until return to baseline or stabilization of event.

Document AEs from the first study intervention, Study Day 1, through the end of treatment. Beyond 30 days after the last intervention, only adverse events which are serious and related to the study intervention need to be recorded.

An abnormal laboratory value will be considered an AE if the laboratory abnormality is characterized by any of the following:

**Abbreviated Title:** Neoadjuvant ADT & Enzalutamide

**Version Date:** 01/25/2024

- Results in discontinuation from the study
- Is associated with clinical signs or symptoms
- Requires treatment or any other therapeutic intervention
- Is associated with death or another serious adverse event, including hospitalization.
- Is judged by the Investigator to be of significant clinical impact
- If any abnormal laboratory result is considered clinically significant, the investigator will provide details about the action taken with respect to the test drug and about the patient's outcome.

**End of study procedures:** Data will be stored according to HHS, FDA regulations, and NIH Intramural Records Retention Schedule as applicable.

The NCI investigators will be responsible for the collection, maintenance, and quality control of the study data. Clinical data will be entered into a data capture system provided by the NCI CCR at least once every two weeks when patients are enrolled on the trial. Protocol-specific eCRFs will be developed for this trial. All data will be kept secure.

Only the following adverse events will be recorded on the Case Report Form:

- Grade 2 unexpected events that are possibly, probably or definitely related to the study drugs;
- Grade 3 and 4 events;
- Grade 5 events regardless of attribution;
- Serious Events regardless of attribution;
- Surgical side effects will be collected at the post-surgery visit only and not recorded if they occur after that time.

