### **1.10 DOSE MODIFICATIONS**

#### **1.10.1 Enzalutamide Dose Modification**

If a patient experiences a  $\geq$  Grade 3 non-hematologic toxicity (except hypertension) attributable to enzalutamide or an intolerable side effect attributable to enzalutamide, withhold dosing for up to 1 month or until symptoms improve to  $\leq$  Grade 2, then resume at the same dose if clinically appropriate. If toxicity recurs and or in the judgment of the investigator dose reduction is appropriate, lower dose levels (120 mg /DL-1 or 80 mg/DL-2), may be considered. Enzalutamide may be discontinued if toxicity recurs and dose modification is no longer clinically appropriate.

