### **1.16.1 Criteria for removal from protocol therapy**

- Completion of protocol therapy
- Participant requests to be withdrawn from active therapy
- Unacceptable Toxicity (Section [3.3.1](#)).
- Investigator discretion

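### The CRF adverse-event list omits non-serious Grade 1 and non-serious expected Grade 2 events, so an enzalutamide hold, reduction or stop for such an event can have no matching entry in the CRF adverse-event data

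*Combined protocol and SAP*

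**What the plan says.** Section 1.19 introduces its list with "Only the following adverse events will be recorded on the Case Report Form". The entries are "Grade 2 unexpected events that are possibly, probably or definitely related to the study drugs", then "Grade 3 and 4 events", Grade 5 events whatever their cause, and "Serious Events regardless of attribution". A last entry covers surgical side effects at the post-surgery visit.

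The same section also says that adverse events are documented from Study Day 1 to the end of treatment and followed to resolution or stabilization at every severity. For a clinically significant laboratory result, the investigator must describe what was done with the drug. Study-specific eCRFs are to be developed; their content is not described.

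Section 1.10.1 gives two triggers for withholding enzalutamide. One is Grade 3 or higher non-hematologic toxicity, other than hypertension, attributed to the drug. The alternative is "or an intolerable side effect attributable to enzalutamide, withhold dosing for up to 1 month or until symptoms improve to" Grade 2 or lower. Dosing then resumes at the same level if clinically appropriate. A later step reads "If toxicity recurs and or in the judgment of the investigator dose reduction is appropriate, lower dose levels" may be considered, and discontinuation is possible if toxicity recurs. Section 1.10.1.1 separately provides for doses missed for scheduling or logistical reasons.

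**The concern.** The recording rule and the dosing rule use different thresholds. The recording rule sorts events by grade, expectedness and seriousness. The second dosing trigger depends on whether the man can tolerate the effect and whether enzalutamide caused it. Nothing in the CRF list refers to the effect of an event on treatment, so some of the low-grade events that matter most for tolerability are left out.

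Three things are at stake. A toxicity table built from the CRF would miss lower-grade effects that limited treatment, although Section 1.20 makes every patient evaluable for toxicity from the first enzalutamide dose. A toxicity hold could not be told apart from a logistical gap using the adverse-event data. And where reduction or discontinuation follows a recurrence, the adverse-event data might not show the first episode. The reason for shortened exposure would also help in interpreting the exploratory response and resistance comparisons in the Statistical Considerations.

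**Working it through.** The plan has no figure on this point. Its one sample-size probability does reproduce: for at least 10 of 50 patients at a rate of 25%, the exact binomial tail is 0.8363, against 83.6% stated. Nothing below depends on it.

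**Step 1: set the two rules side by side.**

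| Event | Can it lead to a hold under 1.10? | On the CRF list in 1.19? |
|---|---|---|
| Grade 3 or higher, non-hematologic, not hypertension, attributed to enzalutamide | Yes, first trigger | Yes |
| Hypertension, Grade 3 or 4 | Yes, under its own rule (1.10.2) | Yes |
| Serious, any grade, intolerable and attributed | Yes | Yes |
| Grade 2, unexpected, intolerable and attributed | Yes, second trigger | Yes |
| Grade 2, expected, not serious, intolerable and attributed | Yes, second trigger | **No** |
| Grade 1, not serious, intolerable and attributed | Yes, second trigger | **No** |
| Grade 2, not serious, unrelated | No, not attributed | No, without consequence here |

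**Step 2: locate the gap.** Grade 3 or higher non-hematologic toxicity is already caught by the first trigger. Outside hypertension and hematologic toxicity, the second trigger therefore adds only Grade 1 and 2 events. Of these, the CRF list keeps the serious ones and the unexpected Grade 2 ones. Enzalutamide is a commercially obtained, approved drug (Sections 1.30 and 1.36), so its known effects would ordinarily count as expected. Non-serious known effects below Grade 3 are the ones omitted.

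**Step 3: illustrate the size.** The documents give no rate, so *q* is an assumption: the share of men with an enzalutamide change for an event outside the list. With 50 men, treated as independent, the expected number is 50 × *q* and the chance of at least one is 1 − (1 − *q*)^50.

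| Assumed *q* | Expected men | Chance of at least one |
|---|---|---|
| 1% | 50 × 0.01 = 0.5 | 1 − 0.99^50 = 39% |
| 2% | 50 × 0.02 = 1.0 | 1 − 0.98^50 = 64% |
| 5% | 50 × 0.05 = 2.5 | 1 − 0.95^50 = 92% |
| 10% | 50 × 0.10 = 5.0 | 1 − 0.90^50 = 99% |

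The number of men is small throughout. From 2% upward, at least one such case is more likely than not.

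**The case against.** Short adverse-event capture is a defensible choice here. This is an exploratory imaging and genomics pilot using an approved drug. All Grade 3 to 5 and all serious events are recorded. No toxicity objective or analysis is specified in Section 1.1 or in the Statistical Considerations. The team discusses each patient weekly and the principal investigator reviews adverse-event data (Section 1.25.1). Status changes go through a registration SOP (Section 1.5), and unacceptable toxicity is a listed reason for leaving therapy (Section 1.16.1), so a reason for discontinuation may well be recorded there. All of this stands, and it limits the consequence.

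It also rules out some stronger readings. A reader might infer that dose changes will have no recorded cause at all. The documents do not support that: events of every severity must be documented and followed, so the cause should be in source records, and for clinically significant laboratory results the action taken with the drug is described as well. Nor do the documents state or rule out a reason field on a dosing eCRF. A reader might also take any intolerable effect to lead straight to a lower dose. The text requires attribution to enzalutamide, calls first for a hold with resumption at the same dose, and makes reduction a later option.

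What the objection does not remove is the explicit exclusion in the CRF list. Source notes are not an analysis dataset, and a reason field is only a possibility.

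**Conclusion.** The point holds as a limited gap in data capture. Followed as written, Sections 1.19 and 1.10.1 allow a toxicity-driven hold, reduction or stop of enzalutamide with no corresponding event in the CRF adverse-event data. The conclusion rests on the word that makes the list exclusive and on the absence of a grade floor in the second trigger. It does not assume anything about the unseen eCRFs: a reason field there would narrow the gap, but would not by itself place the graded event in the adverse-event data.

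The size is unknown. About 0.5 to 5 men of 50 is an illustration under an assumed 1% to 10%, not an estimate. It would be too strong to say that the trial's tolerability results will be understated, because no such analysis is planned; the effect would arise in whatever toxicity summary is drawn from the CRF. The primary objective and sample size are untouched. The change is worth making because it is cheap and amends a stated exclusion.

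**What to change.** Add one entry to the CRF list in Section 1.19: *any adverse event, of any grade, expected or not, that leads to a hold, dose reduction or discontinuation of enzalutamide, to discontinuation of ADT, or to removal from protocol therapy.* Link each such entry to the dosing record, so that toxicity holds can be separated from the logistical gaps in Section 1.10.1.1. For ADT the entry names discontinuation only, because Section 1.9.2 permits no goserelin dose modification.

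When making the change, check whether the dosing eCRF already has a reason-for-change field; if it does, the link can be built on it.

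The cost is one line in the protocol, one link field in the eCRF and a few more adverse-event entries. No dose rule, visit or procedure changes.

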## 1.20 RESPONSE CRITERIA

For the purposes of this study, patients will be monitored for response via endorectal MRI for research purposes, but there will be no formal radiographic assessment of clinical response. It is anticipated that all patients will have a stable or declining PSA throughout the study (prior to surgery) and thus additional response assessments are not required.

Index lesions identified on mpMRI will be entered into a data capture system provided by the NCI CCR.

In the rare case that patients develop a rising PSA while on this study appropriate imaging studies will be performed at the discretion of the treating physician.

Definitions:

Evaluable for toxicity: All patients will be evaluable for toxicity from the time of their first treatment with enzalutamide.

Evaluable for objective response: As described in the first paragraph above, patients will be followed for PSA and changes on endorectal MRI for research purposes only.

**Abbreviated Title:** Neoadjuvant ADT & Enzalutamide

**Version Date:** 01/25/2024

### **1.20.1 Disease Parameters**

All patients will be required to have pathologically proven prostate cancer at enrollment and confirmation that they do not have metastatic disease.

### **1.21 TOXICITY CRITERIA**

The following adverse event management guidelines are intended to ensure the safety of each patient while on the study. The descriptions and grading scales found in the revised NCI Common Terminology Criteria for Adverse Events (CTCAE) version 4.0 will be utilized for AE reporting. All appropriate treatment areas should have access to a copy of the CTCAE version 4.0. A copy of the CTCAE version 4.0 can be downloaded from the CTEP web site ([http://ctep.cancer.gov/protocolDevelopment/electronic\\_applications/ctc.htm#ctc\\_40](http://ctep.cancer.gov/protocolDevelopment/electronic_applications/ctc.htm#ctc_40)).

## **NIH REPORTING REQUIREMENTS / DATA AND SAFETY MONITORING PLAN**

### **1.22 DEFINITIONS**

Please refer to definitions provided in Policy 801: Reporting Research Events found at: <https://irbo.nih.gov/confluence/pages/viewpage.action?pageId=36241835#Policies&Guidance-800Series-ComplianceandResearchEventReportingRequirements>.

### **1.23 OHSRP OFFICE OF COMPLIANCE AND TRAINING / IRB REPORTING**

#### **1.23.1 Expedited Reporting**

Please refer to the reporting requirements in Policy 801: Reporting Research Events and Policy 802 Non-Compliance Human Subjects Research found at: <https://irbo.nih.gov/confluence/pages/viewpage.action?pageId=36241835#Policies&Guidance-800Series-ComplianceandResearchEventReportingRequirements>.

#### **1.23.2 IRB Requirements for PI Reporting at Continuing Review**

Please refer to the reporting requirements in Policy 801: Reporting Research Events found at: <https://irbo.nih.gov/confluence/pages/viewpage.action?pageId=36241835#Policies&Guidance-800Series-ComplianceandResearchEventReportingRequirements>.

